The disappearance of all nontarget lesions and undetectable PSA tumor marker levels. To be assigned a status of complete response, changes in tumor measurements must be confirmed by repeat assessments performed **no less than four weeks** after the criteria for response are first met.

b. Incomplete Response/Stable Disease (SD)

The persistence of one or more nontarget lesion(s) and/or the persistence of detectable serum PSA tumor marker levels. To be assigned a status of stable disease, measurements must have met the stable disease criteria at least once after study entry at a minimum interval of 12 weeks.

c. Progressive Disease (PD)

The appearance of one or more new lesion(s) and/or unequivocal progression of existing nontarget lesions.

NOTE: For lesions only detectable by bone scan (or NaF PET/CT), the appearance of ≥ 2 new lesions, with symptoms, will constitute disease progression. Without symptoms, and if no other evidence of disease progression (no progressive disease by PSA or measurable disease criteria), progression must be documented with repeat bone scintigraphy (or NaF PET/CT) at least 6 weeks later demonstrating ≥ 2 new lesions. This is to eliminate the possibility of flair responses seen on bone imaging scans.

3. Symptomatic Deterioration

Patients with a global deterioration of health status requiring discontinuation of treatment without objective evidence of disease progression at that time should be classified as having symptomatic deterioration.

4. PSA Progression

While PSA values will be collected, and PSA kinetics (PSA responses and maximal changes in PSA by waterfall plots) monitored as secondary endpoints, PSA rise will not be used to determine objective disease progression. Similar to the radiographic studies above, PSA progression or response will be defined using both pre-treatment (study entry) and 3-month values as baseline values.

- a. **PSA Complete Response:** Decrease in PSA to <0.2 ng/mL and confirmed with PSA measurement a minimum of four weeks later (confirmed PSA CR). There must be no evidence of radiographic progression.
- b. **PSA Partial Response:** Greater than or equal to 50% reduction in baseline PSA. There must be no evidence of radiographic progression.
- c. **Best Response:** This is calculated from the sequence of objective statuses. The date of response will be defined as the first date at which PSA declined from baseline or normalized.

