 - i. **Confirmed PSA PR:** Two or more objective statuses of PSA PR or better a minimum of four weeks apart documented before progression. Best response for objective disease must be stable/no response or better.
 - ii. **Unconfirmed PSA PR:** One objective status of PSA PR documented before progression, but not qualifying for confirmed PSA PR. Best response for objective disease must be Stable/no response or better.
 - iii. **No PSA Response:** Objective PSA status does not qualify as a PSA PR or unconfirmed PSA PR.

iv. **Inadequate Assessment, response unknown:** When best response for objective disease is inadequate or unknown or when PSA has been inadequately assessed, then PSA response will be coded likewise.

d. **PSA Progression:** Although not considered progression per the primary objective of this study, time to PSA progression will be used for secondary analyses. PSA progression will be defined as a **50%** increase in PSA over the nadir PSA, and ≥ 2 ng/mL above the nadir, confirmed by a second value 3 or more weeks later (i.e. confirmed rising trend). If no on-study reduction has occurred, nadir would be the baseline value (pre-treatment or month 3 time point for analyses).

C. Evaluation of Patient’s Best Overall Response

The best overall response is the best response recorded from baseline until disease progression/recurrence, taking as reference for progressive disease the smallest measurements recorded after baseline. The table below provides overall responses for all possible combinations of tumor responses in target and nontarget lesions, with or without new lesions.

To be assigned a status of complete or partial response, changes in tumor measurements must be confirmed by repeat assessments performed **no less than four weeks** after the criteria for response are first met.

To be assigned a status of stable disease, measurements must have met the stable disease criteria at least once after study entry at a minimum interval of 12 weeks.

Overall Response for all Possible Combinations of Tumor Response

Target Lesions	Nontarget Lesions	New Lesions	Overall Response
CR	CR	No	CR
CR	Incomplete response/SD	No	PR
PR	Non-PD	No	PR
SD	Non-PD	No	SD
PD	Any	Yes or No	PD
Any	PD	Yes or No	PD
Any	Any	Yes	PD

CR = complete response; PR = partial response; SD = stable disease; PD = progressive disease

1. First Documentation of Response

The time between initiation of therapy and first documentation of PR or CR.

2. Confirmation of Response

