3. Baseline research leukapheresis (50-100 mL approximate total volume, for immunological monitoring) – to take place within 4 weeks prior to day 1.
NOTE: For patients unable to undergo leukapheresis at this time point, a 200-cc blood draw may be substituted (twenty 10-mL green-top heparinized tubes).
4. Tetanus immunization (to take place after baseline leukapheresis and prior to day 1)
5. 20 mL peripheral blood (red-top tubes) for sera to evaluate baseline antibody responses, and 20 mL peripheral blood (green-top tubes) for CTC baseline evaluation
6. FLT PET/CT scan (to occur within 4 weeks prior to day 1).
7. Tissue biopsy – metastatic site – to take place within 2 weeks prior to day 1

C. Immunization #1 (Day 1)

1. Physical examination, symptoms assessment, and ECOG performance score
2. Blood draw for CBC, differential and platelets, chemistry panel, PSA and PAP
3. Subjects will receive pTVG-HP DNA immunizations intradermally on the deltoid area of the lateral arm (preferentially left arm) with 0.25 mL administered at each of two adjacent sites.

4. Following vaccinations, the subjects will be observed for 60 minutes for unanticipated adverse events.
- D. ARM 1 SUBJECTS ONLY: Anti-PD-1 #1 (Day 1, 1-3 hours after day 1 immunization)
1. Pembrolizumab 2 mg/kg administered intravenously over 30 minutes
 2. Subjects will be observed for additional 30 minutes for unanticipated adverse events. Vital signs (temperature, heart rate and blood pressure) will be assessed and recorded by the staff prior to, and at the end of, the treatment period.
- E. Immunization #2 - Day 15 (+/- 3 days)
1. Subjects will receive pTVG-HP DNA immunizations intradermally on the deltoid area of the lateral arm (preferentially left arm) with 0.25 mL administered at each of two adjacent sites.
 2. Following vaccinations, the subjects will be observed for 60 minutes for unanticipated adverse events.
- F. ARM 1 SUBJECTS ONLY: Anti-PD-1 #2 - Day 22 (7 +/- 3 days after day 15 visit)
1. Physical examination, symptoms assessment, and ECOG performance score
 2. Blood draw for CBC, differential and platelets, chemistry panel, PSA and PAP
 3. Pembrolizumab 2 mg/kg administered intravenously over 30 minutes
 4. Subjects will be observed for additional 30 minutes for unanticipated adverse events. Vital signs (temperature, heart rate and blood pressure) will be assessed and recorded by the staff prior to, and at the end of, the treatment period.

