- G. Immunization #3 - Day 29 (14 +/- 3 days after day 15 visit)
1. Subjects will receive pTVG-HP DNA immunizations intradermally on the deltoid area of the lateral arm (preferentially left arm) with 0.25 mL administered at each of two adjacent sites.
 2. Following vaccinations, the subjects will be observed for 60 minutes for unanticipated adverse events.
- H. Immunization #4 - Day 43 (14 +/- 3 days after day 29 visit)
1. Physical examination, symptoms assessment, and ECOG performance score
 2. Blood draw for CBC, differential and platelets, chemistry panel, PSA and PAP
 3. 10 ml peripheral blood (red-top tubes) for sera to evaluate antibody responses, and 100 ml peripheral blood (green-top heparinized tubes) for T-cell response evaluation and CTC analysis
 4. Subjects will receive pTVG-HP DNA immunizations intradermally on the deltoid area of the lateral arm (preferentially left arm) with 0.25 mL administered at each of two adjacent sites.
 5. Following vaccinations, the subjects will be observed for 60 minutes for unanticipated adverse events.

- I. ARM 1 SUBJECTS ONLY: Anti-PD-1 #3 (Day 43, 1-3 hours after day 43 immunization)
1. Pembrolizumab 2 mg/kg administered intravenously over 30 minutes
 2. Subjects will be observed for additional 30 minutes for unanticipated adverse events. Vital signs (temperature, heart rate and blood pressure) will be assessed and recorded by the staff prior to, and at the end of, the treatment period.
- J. Immunization #5 - Day 57 (14 +/- 3 days after day 43 visit)
1. Subjects will receive pTVG-HP DNA immunizations intradermally on the deltoid area of the lateral arm (preferentially left arm) with 0.25 mL administered at each of two adjacent sites.
 2. Following vaccinations, the subjects will be observed for 60 minutes for unanticipated adverse events.
- K. ARM 1 SUBJECTS ONLY: Anti-PD-1 #4 – Day 64 (7 +/- 3 days after day 57 visit)
1. Physical examination, symptoms assessment, and ECOG performance score
 2. Blood draw for CBC, differential and platelets, chemistry panel, PSA and PAP
 3. Pembrolizumab 2 mg/kg administered intravenously over 30 minutes
 4. Subjects will be observed for an additional 30 minutes for unanticipated adverse events. Vital signs (temperature, heart rate and blood pressure) will be assessed and recorded by the staff prior to, and at the end of, the treatment period.
- L. Immunization #6 - Day 71 (14 +/- 3 days after day 57 visit)

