F.4.3. Objective Response Rate and PSA Response Rate

The objective response rate and PSA response rate will be calculated for each study arm and for both arms combined along with the corresponding 95% confidence intervals. The Wilson score method will be used to construct the confidence intervals. Fisher's exact test will be used to compare the objective response and PSA response rates between study arms. Duration of response will be analyzed using the Kaplan-Meier method.

F.5. Analysis of Secondary Endpoints

F.5.1. PAP-Specific Immune Response

The number and frequencies of PAP-specific immune responses will be summarized in tabular format for each study arm and both study arms combined. A log-linear model will be used to evaluate whether PAP-specific immune response predicts the 6-months progression-free survival rate. The interaction between treatment (pembrolizumab administered sequentially versus delayed) and PAP-specific immune response will be included in the model. Analogously, a Cox proportional hazard regression model will be used to examine the association between PAP-specific immune response and the time to radiographic progression.

F.5.2. PAP-Specific T-Cell Response, PD-1 Expression, PD-L1 Expression

PD-1 and PD-L1 expression levels will be summarized in terms of means, standard deviations and ranges for each study arm separately and for both arms combined. The number and frequencies of PAP-specific T-cell responses will be summarized in tabular format. Fisher's exact test will be used to compare the PAP-specific T-cell response rates between study arms. A linear regression model or a negative binomial regression model will be utilized to evaluate the effects of schedule (concurrent versus delayed administration of pembrolizumab) on PD-1 expression on the number of circulating T cells, and PD-L1 expression on the number of circulating epithelial cells. The

choice of the model will be dependent on the distribution of the outcome variables (number of circulating T-cells and number of circulating epithelial cells).

F.6. Exploratory Analyses

F.6.1. Evaluation of Treatment Effects on the Number of Circulating Tumor Cells

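### Arm 1 has two early PSA draws (Days 22 and 64) that Arm 2 lacks, which tilts maximal PSA change toward Arm 1 and PSA progression against it when measured from the pre-treatment baseline

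*Combined protocol and SAP*

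**What the plan says.** **Schedule (Section 9 and the two study calendars).** Item F is headed "ARM 1 SUBJECTS ONLY: Anti-PD-1 #2 - Day 22 (7 +/- 3 days after day 15 visit" and item K, also for Arm 1 only, falls on "Day 64 (7 +/- 3 days after day 57 visit". Both visits include "Blood draw for CBC, differential and platelets, chemistry panel, PSA and PAP". The same draw is made in both arms at "Immunization #4 - Day 43 (14 +/- 3 days after day 29 visit", and PSA is drawn in both arms at Day 85. The Arm 2 calendar has no Day 22 or Day 64 visit. From Day 85 to month 12 the PSA draws are the same in both arms.

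**Definitions (Section 7.B.4).** The plan has "PSA kinetics (PSA responses and maximal changes in PSA by waterfall plots) monitored as secondary endpoints". PSA partial response is a fall of at least 50% from baseline. An unconfirmed response needs only "One objective status of PSA PR documented before progression", and a confirmed one needs two values at least four weeks apart. PSA progression is a 50% rise over the nadir, at least 2 ng/mL above it, confirmed three or more weeks later. Both the pre-treatment and the 3-month values serve as baselines.

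**Analysis.** In F.4.3, Fisher's exact test is "used to compare the objective response and PSA response rates between study arms"; the section does not say whether unconfirmed PSA responses count. No between-arm test is named for maximal change or time to PSA progression, but F.1 expects many clinical and laboratory comparisons between the two arms. Nothing limits PSA analyses to common visits.

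**The concern.** Maximal change is the lowest of the values that happen to be available, and time to progression is the first qualifying date among the draws. Both depend on how often and when PSA is measured. Arm 2's draw days are a subset of Arm 1's. On one and the same PSA curve, the best value read on Arm 1's days can therefore never be worse than the one read on Arm 2's days, and a rise will usually be seen sooner.

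Schedule is what the randomized comparison is meant to test. If the waterfall plots are set side by side, part of any advantage of concurrent over sequential treatment would come from the visit calendar. Time to PSA progression would be distorted in the opposite direction, so the two secondary measures could appear to disagree for no biological reason.

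**Working it through.** **1. The plan's own figures.** No power or sample-size figure is stated for PSA. The stated 15 per arm is for 6-month progression-free survival. It reproduces (Fisher's exact test, one-sided 0.10, 25% v 70%: power 0.823) and is not in dispute here.

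**2. Count of draws after Day 1.**
- Arm 1: Days 22, 43, 64, 85, 106, 127, 148, 169, months 9 and 12 = 10
- Arm 2: Days 43, 85, 106, 127, 148, 169, months 9 and 12 = 8
- Through Day 85: 4 against 2
- Pairs at least four weeks apart by Day 85 (needed for a confirmed response): 22/64, 22/85 and 43/85 in Arm 1, but only 43/85 in Arm 2

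**3. Hand calculation without measurement error.** Assume PSA doubles every T days in both arms (T is not in the documents). Change on day d = 2^((d−1)/T) − 1. For a steadily rising PSA, the best value is the first one drawn.
- T = 90: Arm 1, Day 22: 2^(21/90) − 1 = +17.6%. Arm 2, Day 43: 2^(42/90) − 1 = +38.2%. Gap 20.6 points.
- T = 180: +8.4% against +17.6%. Gap about 9 points.

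A 50% rise is reached T × log2(1.5) = 0.585T days after Day 1.
- T = 90: 52.6 days, about Day 54. The first draw after that is Day 64 in Arm 1 (confirmable on Day 85, 21 days later) and Day 85 in Arm 2. Gap 21 days.
- T = 180: 105.3 days, just after Day 106. Both arms first show it on Day 127, so there is no gap.

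**4. Simulation with identical PSA curves in both arms.** 200,000 patients per setting, mean doubling time 90 or 180 days, log-scale measurement SD 0.10 or 0.20, draws to month 12. The 2 ng/mL part of the progression rule is not applied.

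| Doubling, SD | Median best change, Arm 1 v Arm 2 | Gap (points) | Median time to PSA progression (day) | Single-value ≥50% response |
|---|---|---|---|---|
| 90 d, 0.10 | +15.7% v +38.4% | 22.7 | 64 v 85 | 10.3% v 10.3% |
| 90 d, 0.20 | +7.3% v +32.0% | 24.7 | 64 v 85 | 11.3% v 11.2% |
| 180 d, 0.10 | +3.6% v +14.9% | 11.3 | 106 v 127 | 6.4% v 6.4% |
| 180 d, 0.20 | −6.9% v +5.4% | 12.3 | 85 v 106 | 8.3% v 8.0% |

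A separate run at 3-month doubling and 15% CV, to month 12 and with confirmation of progression required, gives median best change of +14% v +38% and progression at Day 64 v Day 85.

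**5. Other assumed courses.** With flat PSA, the one-year gap in best change is only 2 to 3 points and median PSA progression is not reached. With a transient dip in 30% or 60% of patients, the gap in best change is about 14 to 18 points and median progression is equal. The largest shift in single-value ≥50% response in these runs is 15.2% v 12.3% by Day 85 (2.9 points). The largest shift in confirmed response is 1.2 points.

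**6. Common visits only.** With Days 43, 85, 106, 127, 148, 169 and months 9 and 12 used in both arms, the counts are 8 and 8, and the schedule-induced difference is zero by construction.

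**The case against.** The strongest objection is that the only between-arm PSA test the plan names is almost untouched. One patient in 15 is 6.7 points, so a shift of 2.9 points is less than half a patient. For assumed true response rates of 10%, 20% and 30%, that shift moves the false-positive rate of a two-sided 0.05 Fisher test with 15 per arm from 0.6%, 1.7% and 1.7% to 0.9%, 1.9% and 1.8%. This stands, and the point should not be read as a serious bias in the F.4.3 test.

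Maximal change and time to PSA progression have no named between-arm test. This also stands, but they are declared secondary measures and F.1 anticipates comparing many measurements between arms, so a comparison of them is foreseeable.

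A further objection is that stopping the count at Day 85 and ignoring confirmation exaggerates the effect. Carrying draws to month 12 and requiring confirmation does not remove it (working, step 4).

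Finally, discarding real on-treatment Arm 1 values from a primary-objective response rate goes too far for so small a shift, since it could drop a genuine response or its confirming value. This is accepted, and the fix keeps those values.

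A reader might also infer that the rationale for Arm 4 in Section 2.F is affected, because it rests on how many patients had any PSA decline. The documents do not support that. The comparison there is Arm 3 with Arm 1, and Arm 3's draws at Weeks 3, 6, 9 and 12 fall on Days 22, 43, 64 and 85, the same as Arm 1. Any decline is also not an endpoint defined in Section 7.

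**Conclusion.** The point holds for maximal PSA change and time to PSA progression measured from the pre-treatment baseline. With no treatment difference, the calendar alone lowers Arm 1's median best change by about 12 to 25 percentage points under 3- to 6-month doubling and 10-20% variation (11.3 to 24.7 in the runs tabulated). It brings PSA progression forward in Arm 1 by up to about 21 days.

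The direction for best change follows from the nested draw days and needs no assumption. The sizes rest on assumed PSA kinetics that the documents do not give, and they shrink to 2 to 3 points for best change if PSA is flat.

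The ≥50% response rate in F.4.3 moves by about 0 to 4 points on a single value and less if confirmed. Month-3-baseline analyses are unaffected. It would be tempting to describe the arms as four against two values throughout, but that is true only to Day 85; over the year it is 10 against 8.

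**What to change.** In the detailed analysis plan that F.1 promises, state that:

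- Arm 1 versus Arm 2 comparisons of maximal PSA change and time to PSA progression from the pre-treatment baseline use only visits scheduled in both arms: Days 1, 43, 85, 106, 127, 148, 169 and months 9 and 12.
- The Day 22 and Day 64 values are shown descriptively for Arm 1.
- The F.4.3 PSA response rate keeps all values, with a common-visit sensitivity analysis beside it. The plan should also say whether unconfirmed responses count.

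No visit, treatment or sample size changes. The cost is some wording, and two Arm 1 values per patient that are not used in those secondary between-arm comparisons.

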The primary endpoints of the trial will be clinical endpoints (safety, 6 month PFS, and objective response rates). All subjects will undergo radiographic imaging (CT of abdomen and pelvis and bone scan) prior to treatment, and at 3-month intervals (or as clinically indicated). Radiographic disease progression and response will be defined using PCWG2 published criteria [65], and as detailed in Section 7. Based on the prior trials leading to the approval of sipuleucel-T, and because immune therapies are expected to require up to several months before radiographic responses or stabilization might be observed, the radiographic studies obtained at 3 months will not be used to define progression, rather will be used as the baseline for future comparison. That is, while baseline studies will be obtained prior to study registration, and radiographic progression may be expected in 50% of patients at 3 months, this will not be used to define progression necessitating patients come off study, rather disease progression occurring after this initial 3-month period. These criteria, in addition to being more standard for contemporary clinical trials in advanced prostate cancer, were also specifically designed to capture late radiographic objective responses that have been observed with immune-based therapies, including pembrolizumab and other T-cell checkpoint inhibitors [80]. Time to progression will be determined from registration for all subjects. 6-month progression-free survival will be calculated for each treatment arm, as well as the median progression-free survival.

The primary endpoint for the extended treatment Arms 3 and 4 will be time to radiographic progression.

7. Measurement of Effect (PCWG2 Recommendations)

A. Malignant Disease Evaluation

To assess objective response, it is necessary to estimate the overall tumor burden at baseline (for purposes of comparison, “baseline” imaging will be that obtained at 3-month time point) to which subsequent measurements will be compared. Measurable disease is defined by the presence of at least one measurable lesion.

All measurements should be recorded in metric notation by use of a ruler or calipers. The same method of assessment and the same technique should be used to characterize each identified lesion at baseline and during follow-up. All pre-treatment evaluations should be performed as closely as possible to the beginning of treatment and not more than four weeks before registration.

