All subjects will be assessed at regular intervals, as per the study calendar, for evidence of adverse events by exam, symptoms, and clinical laboratory findings. For these assessments, we will use the NCI common terminology criteria, version 4 (http://ctep.cancer.gov/protocoldevelopment/electronic_applications/docs/ctcae_v4.pdf).

B. Immunological Monitoring

Blood will be collected by either peripheral blood draw (up to 120 mL), leukapheresis (50-100 mL), or leukapheresis replacement draw (200 mL) pre-immunization, at weeks 6, 12 and 24 of treatment, and at months 9 and 12 (quarterly intervals up to one year), for immunological monitoring. From the heparinized blood, peripheral blood mononuclear cells (PBMC) will be prepared by density centrifugation over Ficoll-Paque using standard techniques. PBMC will be used directly for analysis, and residual material cryopreserved in liquid nitrogen using 90% autologous serum collected at the time of blood draw, or 90% fetal calf serum, and 10% DMSO. Sera will be prepared from the red-top tubes and stored in aliquots at -80°C for antibody analyses. IFN γ and granzyme B ELISPOT analysis, PAP-specific T-cell proliferation, flow cytometric assays of antigen-specific cytokine secretion, and ELISA tests for antigen-specific antibodies, will be the primary methods of analysis. The primary antigens tested will be PAP (experimental), PSA (negative control), and tetanus toxoid (positive control). The primary immune analysis will be

conducted at the 6-month time point, and compared with the pre-treatment time point, and for patients to be evaluable for immune response (primary endpoint), blood (PBMC and serum) from this time point must be available for analysis. However, immune monitoring will be conducted at the other time points indicated in secondary analyses to evaluate kinetic measures of immunity, and evaluate whether durable immune responses of particular phenotypes are elicited and/or maintained. Assays may be conducted at the time of sample collection (fresh) and/or batched and performed at one time from multiple cryopreserved samples collected at different time points. Other methods of effector and regulatory T-cell response to PAP and other human tissue antigens may be used.

B.1. Quantitative assessment of PAP-specific CD8+ T-cell effector immunity

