The expected 6-months progression-free survival rate in Arm 2 (pembrolizumab is administered sequentially after pTVG-HP) is 25%. It is hypothesized that the treatment of pTVG-HP, when administered concurrently with pembrolizumab (Arm 1), will result in a substantial increase in the 6-month progression-free survival rate. Specifically, it is anticipated that the 6-month progression-free survival rate in Arm 1 will be at least 65-75%. The following table shows the required sample sizes for detecting various differences in the 6-month progression-free survival rates between the two study arms, assuming 80% power and a one-sided 0.10 significance level. Since this is a pilot study, a less stringent significance level of 0.10 rather the traditional 0.05 level will be used for the primary efficacy evaluation.

	6-month progression free survival rate Arm 1			
6-month progression free survival rate Arm 2	0.65	0.70	0.75	0.80
0.20	15	11	10	9
0.25	17	15	11	10

A sample size of 15 patients per arm is proposed. This sample size will provide 80% power to detect an anticipated absolute difference of at least 45% (e.g., 25% vs. 70% or 20% vs. 65%) in the 6-months progression free survival rates between the two arms. These calculations are based on Fisher’s exact test. Furthermore, the proposed sample size of 15 patients per arm is also sufficient to provide accuracy in estimating toxicity rates. Specifically, the toxicity rates (i.e., of grade ≥ 2, grade ≥ 3, grade 4 toxicities) for each arm will be estimated with a standard error of less than 15% and the 95% confidence interval of the toxicity rates will be no wider than 45%. The probability of observing at least one event of a serious adverse event within a study arm is >95% if the adverse event rate is 20%. Analogously, the probability of observing at least one event of serious adverse event is at least 79% if the adverse event rate is only 10%.

In order to account for unevaluable (for efficacy evaluation) patients, 32 eligible patients (16 per arm) will be accrued and randomized. Based on past experience with this patient population treated at our institution, we anticipate that the proposed total number of 32 patients will be accrued within 18 months.

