This section outlines the statistical analysis strategy and procedures for the study. Prior to the analysis of the final study data, a detailed Statistical Analysis Plan (SAP) will be written describing all analyses that will be performed.

Summary tabulations will be presented that will display the number of observations, mean, standard deviation, median, range, minimum, and maximum for continuous variables and the number and percent per category for ordinal and categorical data. All endpoints of this study will

be presented graphically where possible using boxplots and histograms for continuous variables and (stacked) bar charts for categorical variables. Data analysis will be performed using SAS[®] (SAS Institute Inc., Cary, North Carolina) version 9.3 or greater.

There are many comparisons made between the two trial arms for multiple measurements, both clinical and laboratory. However, since this a pilot study, no adjustment will be made for multiple comparisons. A two-sided test at a significance level of 0.05 will be used for all comparisons, unless noted otherwise.

F.2. Analysis Populations

The ITT population consists of all patients who are randomized. The per-protocol population consists of all evaluable patients, i.e., patients who have been treated according to protocol (all inclusion/exclusion criteria are satisfied, and adequate treatment compliance (complete treatment to at least day 43). The safety population consists of all subjects who received at least one dose of pTVG HP alone or in combination with pembrolizumab. All primary, secondary and correlative outcomes will be analyzed for both the IIT and per-protocol population. The IIT population will be the primary analysis population. Safety will be evaluated using the safety population.

F.3. Baseline Comparability

All measurements (variables) collected at baseline will be summarized and compared between study arms. These include demographic variables, ECOG PS, lab parameters (CBC, chemistry panel, serum testosterone, PSA and PAP) medical history information and CTCs. Comparisons between study arms of baseline variables on a continuous scale will be performed using a two-sample t-test and/or nonparametric Wilcoxon Rank Sum test. Comparisons between study arms of baseline variables on a categorical scale will be performed using Fisher's exact test.

F.4. Analysis of Primary Endpoints

F.4.1. Analysis of Toxicity Rates and Serum Chemistry Parameters

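### F.5.1 relates a 6-month immune response to 6-month PFS and time to progression with no landmark or time-dependent term, so the marker is taken with, and sometimes after, its outcome (Arms 1 and 2)

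*Combined protocol and SAP*

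**What the plan says.** Section 11.F.5.1 gives two models. The first: "A log-linear model will be used to evaluate whether PAP-specific immune response predicts the 6-months progression-free survival rate", with a treatment-by-response interaction. The second: "a Cox proportional hazard regression model will be used to examine the association between PAP-specific immune response and the time to radiographic progression". It states no visit, landmark or time-dependent term. That response enters as a fixed covariate is an inference, but it is the natural reading of a plain model term.

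Section 10.B supplies the default visit. The primary immune analysis compares 6 months with pre-treatment, and "for patients to be evaluable for immune response (primary endpoint), blood (PBMC and serum) from this time point must be available for analysis". Other visits serve secondary, kinetic analyses, although the response definitions in 10.B.1 to 10.B.3 also admit another post-treatment time point.

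Section 9.Q (Day 169) places the leukapheresis and the CT and bone scan at one visit, each with its own window of 7 days either side. Section 11.F.4.2 runs the clock from randomization and from the 3-month assessment. Section 6.B continues immune draws to one year for patients off study and asks for the 6-month evaluations off study if feasible.

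On populations, Section 11.F.2 says "All primary, secondary and correlative outcomes will be analyzed for both the IIT and per-protocol population" and "The IIT population will be the primary analysis population" (IIT is evidently a slip for ITT).

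**The concern.** A covariate that predicts an outcome must be known before the outcome occurs. Here the default covariate becomes known at month 6, after both time origins and at the visit that can settle the first outcome. A patient who has progressed, or has moved to another therapy, may have a different T-cell response because of it. An association could then run from progression to marker.

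This analysis answers secondary objective 1. PAP-response frequency was also among the reasons given for Arm 4's vaccine schedule (Section 2.F), so an over-read link between immunity and PFS could influence later design.

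A second gap is the population. Section 10.B makes patients without 6-month blood not evaluable, Section 11.F.2 makes ITT primary, and F.5.1 does not say which governs.

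**Working it through.** **Inputs.** Section 11.E: 16 randomized per arm; 6-month PFS of 25% in Arm 2 and 65-75% in Arm 1. F.5.1 has no figure of its own to reproduce. The Section 11.E sample size that uses these rates does reproduce: Fisher's exact test, one-sided 0.10, 15 per arm, gives 82.3% power for 25% against 70%.

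**1. Order of marker and outcome.**

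| Outcome | When it is settled | Where the 6-month draw falls |
|---|---|---|
| 6-month PFS from randomization, Month-3 rule | Day 169 scan, +/- 7 days | Same visit; up to 7 + 7 = 14 days before or after the scan |
| Progression against pre-treatment scans | From the Month-3 scan onward | After it, for early progressors |
| Progression on an unscheduled scan or leading off study before Day 169 | Before Day 169 | After it |
| 6-month rate from the 3-month assessment | About month 9 | Before it, in patients not yet progressed |

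On the second row, Section 6.B says "radiographic progression may be expected in 50% of patients at 3 months".

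**2. Events by or at month 6, from randomization.** Arm 2: 16 x (1 - 0.25) = 12. Arm 1: 16 x (1 - 0.65) = 5.6, down to 16 x (1 - 0.75) = 4. Total 17.6 to 16.0 of 32, or 55% to 50%.

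**3. Share of Cox events through month 12 (constant hazard assumed).** The number of events in an arm by month m is 16 x (1 - S^(m/6)), where S is the 6-month PFS rate.

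- From randomization, by month 12: Arm 2 has 16 x (1 - 0.0625) = 15; Arm 1 has 16 x (1 - 0.4225) = 9.2 or 16 x (1 - 0.5625) = 7. Totals are 24.2 and 22.0. Shares: 17.6/24.2 and 16.0/22.0, both 73%.
- From month 3, with all 32 at risk and the same hazards: by month 6, 8 + 3.1 = 11.1 or 8 + 2.1 = 10.1. By month 12 (9 months), 14 + 7.6 = 21.6 or 14 + 5.6 = 19.6. Shares: 51% and 52%.

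**4. Null error.** Simulations had no true marker effect, 32 patients, an arm-stratified Cox score test at two-sided 0.05 and an assumed, independent detection probability per draw. Monte Carlo error is about 0.4-0.6 points.

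- 6-month sample, unsampled patients excluded as in Section 10.B: 3.8-5.9%, near nominal.
- Unsampled patients counted as non-responders under ITT (20% detection, randomization origin, 3-month median): 4.6% if 25% of Week-12 progressors lack 6-month blood, 7.0% if 50% do.
- Response at any visit counts (20% detection, Month-3 baseline): 5-6% with complete off-study draws, about 7% with half, about 13-14% with none.

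These runs let the marker ignore progression. When progression was assumed to cut detection by 50-80%, the Cox error with the 6-month marker rose to 13-30%, while a Week-12 landmark stayed near 5%. That range depends strongly on the assumed detection rate and is lower when detection is rarer, so it shows direction, not size.

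**5. Precision of a Week-12 landmark.** At 20% detection over two draws, responders number 32 x (1 - 0.8^2) = 11.5, about 12. With Cox information of about 3.0, the 95% limits lie a factor exp(1.96/sqrt(3.0)) = 3.1 either side of the estimate.

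**The case against.** The strongest reply is that this is a matter of wording. Secondary objective 1 and the Cox sentence both speak of association; only the log-linear sentence uses the stronger verb. Section 10.B does fix a visit. Month-3 scans do not define progression, so the first scheduled scan that can do so is Day 169, and marker and outcome mostly coincide. Counted from the 3-month assessment, the 6-month rate falls near month 9, and the marker can precede it. Error is near nominal under the plan's own evaluability rule. This is one unadjusted secondary analysis in a pilot, and Section 11.F.1 promises a detailed SAP.

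All of that stands, and it limits the point. It does not remove it: coincidence is not precedence, and off-study draws reduce missing data without restoring order.

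A reader might infer that the plan carries a gross bias in favour of patients who stay event-free longer. Illustrative false-positive rates of 36-90% arise if response at any visit counts, progression is called from day 1 and draws stop at progression. The documents do not support those conditions: the default is the 6-month sample, progression is defined only after Month 3, and draws continue off study.

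The objection that a Week-12 marker changes the question in Arm 2 is correct and is carried into the fix.

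**Conclusion.** The concern holds as a fault of temporal order in F.5.1 for Arms 1 and 2. The default marker is taken with the outcome in most cases and after it in some. It can support an association with 6-month PFS from randomization but not prediction, and complete sampling would not change that.

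The count of 16 to 17.6 of 32 patients rests only on the planned PFS rates. It includes events found at the Day 169 visit itself, so it is not a count of patients whose event came earlier. The 73% and 51-52% shares also need a constant hazard, and the latter needs all 32 at risk at month 3.

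The documents do not support a claim of inflated type I error under the plan's own rules. Inflation needs response at any visit together with incomplete off-study draws: about 7% with half drawn and 13-14% with none, the last contrary to Section 6.B. Those rates rest on assumed detection probabilities.

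The stakes are moderate. No primary analysis is affected.

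**What to change.** In F.5.1 or the promised SAP, for Arms 1 and 2:

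- (a) For the predictive question, enter response in the Cox model as a time-dependent covariate, positive only from the draw at which it is first detected. And/or use a Week-12 landmark: response by the Day 43 or Day 85 draw against progression from the 3-month assessment (definition 2 in Section 7.C.5), in patients at risk at the later of the Day 85 draw and the Month-3 scan.
- (b) Keep the analysis of 6-month response against 6-month PFS, but report it as an association and replace *predicts*.
- (c) State that the Section 10.B evaluability rule governs this analysis, and do not count unsampled patients as non-responders. Report their number by arm and progression status.

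The cost is wording; the draws, scans and time origin already exist. In simulation both methods in (a) held their level (4.9-6.0% for the landmark, 4.4-5.6% for the time-dependent term).

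The real price is precision: about 20 to 22 events remain for the landmark by month 12 at planned rates, with an interval about threefold either side. The landmark also misses later responses, which the time-dependent term covers. In Arm 2 pembrolizumab starts at Day 85, so Week-12 response mainly reflects vaccine alone. Section 9.M does not require the blood to be drawn before that first dose, so draw dates must be checked. The landmark's treatment interaction therefore answers a different question from the 6-month one and must be read that way.
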